4.2 Exclusion Criteria**4.2.1 Pregnancy or Breast-Feeding**

Pregnant or breast-feeding women will not be entered on this study because there is yet no available information regarding human fetal or teratogenic toxicities. Pregnancy tests must be obtained in girls who are post-menarchal. Males or females of reproductive potential may not participate unless they have agreed to use an effective contraceptive method for the duration of study therapy and for 12 weeks after flotetuzumab discontinuation.

4.2.2 Concomitant Medications

4.2.2.1 Corticosteroids: Patients must be off steroids (unless physiologic replacement dosing) for at least 7 days prior to enrollment. If used to modify **immune adverse events** related to prior therapy, \geq 14 days must have elapsed since last dose of corticosteroid (See [Section 4.1.7.1.d](#)).

4.2.2.2 Investigational Drugs: Patients who are currently receiving another investigational drug are not eligible.

4.2.2.3 Anti-cancer Agents: Patients who are currently receiving other anti-cancer agents are not eligible [except hydroxyurea, which may be continued until 24 hours prior to start of protocol therapy].

4.2.2.4 Anti-GVHD agents post-transplant:

Patients who are receiving cyclosporine, tacrolimus or other agents to treat graft-versus-host disease post bone marrow transplant are not eligible for this trial.

4.2.3 Study Specific:

4.2.3.1 Patient has French-American-British classification (FAB) type M3 leukemia (acute promyelocytic leukemia) or identification of t(15;17).

4.2.3.2 Patient has isolated CNS involvement or isolated extramedullary relapse.

THIS PROTOCOL IS FOR RESEARCH PURPOSES ONLY, SEE PAGE 1 FOR USAGE POLICY

4.2.3.3 Patient with known HIV infection are eligible if he or she has a negative HIV serology and an undetectable viral load.

4.2.3.4 Patient known to have one of the following concomitant genetic syndromes: Bloom syndrome, ataxia-telangiectasia, Fanconi anemia, Kostmann syndrome, Shwachman syndrome or any other known bone marrow failure syndrome. Patients with Down syndrome ARE eligible for the study.

4.2.3.5 Patients must not weigh < 17 kg.

4.2.3.6 Patients must not have received prior therapy with a CD123 directed antibody or CD123 directed CAR T cells.

4.2.4 Infection: Patients who have an uncontrolled infection are not eligible.

4.2.5 Patients who have received a prior solid organ transplantation are not eligible.

4.2.6 Patients who in the opinion of the investigator may not be able to comply with the safety monitoring requirements of the study are not eligible.

4.2.7 Known hypersensitivity to murine, yeast, or recombinant proteins; polysorbate 80; recombinant human serum albumin; benzyl alcohol; or any excipient contained in the flotetuzumab drug formulation. Additionally, those patients who have had a hypersensitivity reaction to etoposide that is considered likely related to polysorbate 80 are not eligible.

4.2.8 Patients must refrain from driving a motor vehicle or operating heavy machinery while receiving flotetuzumab and for 30 days from the date of last study drug administration.

5.0 TREATMENT PROGRAM

5.1 Overview of Treatment Plan

A cycle of therapy is 29 days. Following the end of flotetuzumab infusion on Day 29, patients will be allowed a treatment free interval of up to 3 days to allow respite. The duration of this treatment free interval will be up to the treating physician's discretion. Keeping interruptions to \leq 3 days will reduce the chance of disease rebound and lower the risk for recurrent CRS based upon clinical experience in flotetuzumab-treated adult patients. Alternatively, the treating physician may opt to skip the treatment-free interval and allow the patient to proceed immediately to the next cycle without respite, as long as the patient is experiencing clinical benefit. Clinical benefit may be defined as a reduction in leukemia related symptoms, and/or a reduction in transfusion frequency and/or a reduction or clearance of peripheral blasts. Patients with at least a PR following Cycle 2 may continue on subsequent cycles of flotetuzumab for a total of up to 6 cycles, lasting approximately 6 months. Patients should discontinue protocol therapy if they have not achieved at least a PR following Cycle 2.

During the dose escalation portion of the study, flotetuzumab will be administered by continuous intravenous infusion for a total of 28 days (NOTE: infusion ends on Day 29).

All doses of flotetuzumab in this study are described as nanograms/kg/day. However, the drug labels are expressed in milligrams/mL. Step-up dosing will be used in the first 7 days of Cycle 1 to minimize IRR/CRS, followed by 21 days at the adult recommended phase 2 dose (RP2D) (500 nanograms/kg/day, Dose Level 1 [DL1]). If DL1 is deemed safe and tolerable based on standard immunotherapy DLT assessments ([Section 5.5](#)), an additional cohort of patients will dose-escalate to flotetuzumab at 700 nanograms/kg/day (DL2). Step-up dosing will occur during the first 8 days of Cycle 1 for this cohort. If fewer than 2 DLTs occur at DL2, this will be considered the RP2D. If there are ≥ 2 DLTs at DL2, DL1 will be considered the MTD. If DL1 is not tolerable, dose de-escalation will occur to 300 nanograms/kg/day (DL-1) with initial step-up dosing during the first 8 days of Cycle 1 for this cohort. If DL-1 is deemed tolerable, this dosing will be the MTD. Further dose de-escalation will not be permitted and will limit further exploration of flotetuzumab in this patient population. No planned step-up dosing will occur during subsequent cycles unless there is an infusion interruption of more than 3 days between cycles of flotetuzumab. If an interruption lasts > 3 days, subsequent cycle dosing should be discussed with the study chair.

Bone marrow evaluation will be performed on Day 29 (+/- 1 day) to evaluate response.

Drug doses should be adjusted based on the patient's weight measured within 7 days prior to the beginning of each cycle. Flotetuzumab continuous infusion must be administered through an IV line with a low protein binding polyethersulfone (PES) 0.2 micron in-line filter. Due to the risk of CRS, sites should have sufficient supply of tocilizumab (enough to treat a 70 kg patient x three 8 mg/kg doses) at all times for each patient on therapy. Patients will remain hospitalized for the duration of Cycle 1 for safety monitoring. Patients may receive subsequent cycles as an outpatient if the drug can be accurately and safely delivered (see [Appendix XIV](#)), and at the discretion of the treating physician and after discussion with the study chair.

Patients should receive a single dose of IT cytarabine prior to the start of Cycle 1 between Days -6 to 0. Patients may receive IT cytarabine on Day 1 of subsequent cycles or with bone marrow evaluations at the discretion of the treating physician.

IT Cytarabine Age-based dosing:

Age (yrs)	Dose
< 1	20 mg
1-1.99	30 mg
2-2.99	50 mg
≥ 3	70 mg

Infusion-Related Reaction/Cytokine Release Syndrome (IRR/CRS) Prophylaxis for Cycle 1:

Acetaminophen: 10 – 15 mg/kg/dose (max: 650 mg/dose) IV or PO

Week 1 Step-up Dosing: once daily, 30 minutes prior to starting each new dose, then q4-6h pm

Final Dose Escalation: 30 minutes prior to dose escalation to goal dose, then scheduled q8h x 48 hours, then q4-6h pm

THIS PROTOCOL IS FOR RESEARCH PURPOSES ONLY, SEE PAGE 1 FOR USAGE POLICY

Diphenhydramine: 0.5 – 1 mg/kg/dose (max: 50 mg) IV or PO**Week 1 Step-up Dosing:** once daily, 30 minutes prior to starting each new dose, then q6-8h prn**Final Dose Escalation:** 30 minutes prior to dose escalation, then scheduled q8h x 48 hours, then q6-8h prn**Histamine 2 Receptor Antagonists:**

Ranitidine: 1 mg/kg/dose IV (max single dose: 50 mg) or 2 mg/kg/dose PO (max single dose: 150 mg); or equivalently dosed H2 receptor antagonist (e.g., famotidine 0.25 mg/kg/dose IV (max single dose: 20 mg) or 0.5 mg/kg/dose PO (max single dose: 40 mg))

Week 1 Step-up Dosing: 30 minutes prior to starting each new dose, then ranitidine q8h (IV) or q12h (PO) prn OR famotidine q12h IV/PO prn**Final Dose Escalation:** 30 minutes prior to dose escalation, then scheduled ranitidine q8h (IV) or q12h (PO) OR famotidine q12h IV/PO x 48 hours, then prn (at same frequency)**Dexamethasone****Week 1, Day 1:** 5 mg/m²/dose (max single dose: 5 mg) IV or PO once, 30 minutes prior to starting flotetuzumab, then 5 mg/m²/dose (max single dose: 5 mg) IV or PO given 12 hours later x 1 (total daily dose: 10 mg/m²)

DL1, Cycle 1										
	Day 0	1	2	3	4	5	6	7	8-28	29
IT cytarabine*	X									
Flotetuzumab 30 nanograms/kg/day		X								
Flotetuzumab 60 nanograms/kg/day			X							
Flotetuzumab 100 nanograms/kg/day				X						
Flotetuzumab 200 nanograms/kg/day					X					
Flotetuzumab 300 nanograms/kg/day						X				
Flotetuzumab 400 nanograms/kg/day							X			
Flotetuzumab 500 nanograms/kg/day								X	X	

*can be given between Days -6 and 0

DL-1, Cycle 1											
	Day 0	1	2	3	4	5	6	7	8	9-28	29
IT cytarabine*	X										
Flotetuzumab 30 nanograms/kg/day		X									
Flotetuzumab 60			X	X							

* can be given between Days -6 and 0

	Day 0	1	2	3	4	5	6	7	8	9-28	29
IT cytarabine*	X										
Flotetuzumab 30 nanograms/kg/day		X									
Flotetuzumab 100 nanograms/kg/day			X								
Flotetuzumab 200 nanograms/kg/day				X							
Flotetuzumab 300 nanograms/kg/day					X						
Flotetuzumab 400 nanograms/kg/day						X					
Flotetuzumab 500 nanograms/kg/day							X				
Flotetuzumab 600 nanograms/kg/day								X			
Flotetuzumab 700 nanograms/kg/day									X	X	

*can be given between Days -6 and 0

All Cohorts, Cycles 2+

	Day 1	Day 2-28	29
IT cytarabine*	X		End of flotetuzumab infusion
Flotetuzumab at Cycle 1 target dose	X	X	

*Patients may receive an optional dose of IT cytarabine during subsequent cycles on Day 1 or with bone marrow evaluations at the discretion of the treating physician.

If a treatment-free interval > 3 days occurs between any 2 cycles, the subsequent cycle will require step-up dosing. If a treatment-free interval > 3 days occurs between any 2 cycles, the Study Chair must be notified and the subsequent cycle dosing schedule must be discussed.

IT Cytarabine Age-based dosing:

Age (yrs)	Dose
< 1	20 mg
1-1.99	30 mg

THIS PROTOCOL IS FOR RESEARCH PURPOSES ONLY, SEE PAGE 1 FOR USAGE POLICY

2-2.99	50 mg
≥ 3	70 mg

Infusion Related Reaction/Cytokine Release Syndrome Prophylaxis prior to each subsequent cycle and for prolonged interruptions:

Prophylaxis is required prior to subsequent cycles if the treatment-free interval is greater than 24 hours. Prophylaxis is also recommended following any interruption in cycles that last >24 hours. For interruptions in cycles that last <24 hours, prophylaxis can be given at the discretion of the treating physician.

Acetaminophen: 10 – 15 mg/kg/dose (max: 650 mg/dose) IV or PO
Day 1: 30 minutes prior to starting flotetuzumab infusion, then q4-6h prn

Diphenhydramine: 0.5 – 1 mg/kg/dose (max: 50 mg) IV or PO
Day 1: 30 minutes prior to flotetuzumab infusion, then q6-8h prn

Ranitidine: 1 mg/kg/dose IV (max single dose: 50 mg) or 2 mg/kg/dose PO (max single dose: 150 mg); or equivalently dosed H2 receptor antagonist (e.g., famotidine)
Day 1: 30 minutes prior to starting flotetuzumab infusion, then q8h (IV) or q12h (PO) prn

Dexamethasone

Day 1: 5 mg/m²/dose (max single dose: 5 mg) IV or PO once 30 minutes prior to starting flotetuzumab infusion, then 5 mg/m²/dose (max single dose: 5 mg) IV or PO given 12 hours later (total daily dose: 10 mg/m²)

5.2 Criteria for Starting Subsequent Cycles

A cycle may be repeated every 29 days, with an optional ≤ 3 day respite period between each cycle. The optional ≤ 3 day respite period will be up to the treating physician's discretion. If a patient has progressive disease at any time point or is unable to achieve a PR following Cycle 2, subsequent protocol therapy must be discontinued. Due to a risk for disease rebound and recurrent CRS, patients are allowed to proceed to subsequent cycles while awaiting disease evaluation at the discretion of the treating physician. For patients with no evidence of disease after Cycle 1, subsequent cycles should be interrupted until ANC ≥ 500 μ L and platelets $\geq 20,000/\text{mm}^3$. Patients with persistent disease are permitted to continue flotetuzumab regardless of ANC and platelet counts. Laboratory parameters as defined in the eligibility section, [Section 4.0](#), must be met, and the patient must be eligible to continue agent administration per the requirements in [Section 6.0](#).

5.3 Dose Escalation Schema

5.3.1 Inter-Patient Escalation

The starting dose will be 500 nanograms/kg/day (DL1) with dose levels for subsequent groups of patients as follows:

Dose Level	Dose (nanograms/kg/day)
-1	300
1*	500
2	700

* Starting Dose Level

THIS PROTOCOL IS FOR RESEARCH PURPOSES ONLY, SEE PAGE 1 FOR USAGE POLICY

There will be no planned escalations beyond Dose Level 2 (700 nanograms/kg/day), as previous pediatric Phase 1 studies have rarely defined a MTD greater than 160% of the adult MTD. If estimated clearance is high in this pediatric study population, we will consider amending the protocol to allow further dose escalation to 900 nanograms/kg/day.

If the MTD has been exceeded at the first dose level, then the subsequent cohort of patients will be treated at a dose of 300 nanograms/kg/day (Dose Level -1). If Dose Level -1 is not well tolerated, further de-escalation will not occur. The study will be closed to accrual.

5.3.2 Intra-Patient Escalation

Intra-patient dose escalation will occur during the first 7 days of Cycle 1 on Dose Level 1 and the first 8 days of Cycle 1 on Dose Levels -1 and 2 as described in [Section 5.1](#). Intra-patient dose escalation occurring outside of this time period is not allowed.

5.4 **Grading of Adverse Events**

Adverse events (toxicities) will be graded according to the NCI Common Terminology Criteria for Adverse Events (CTCAE) version 5.0. All appropriate treatment areas should have access to a copy of the CTCAE version 5.0. A copy of the CTCAE version 5.0 can be downloaded from the CTEP website (http://ctep.cancer.gov/protocolDevelopment/electronic_applications/ctc.htm). Any suspected or confirmed dose-limiting toxicity should be reported immediately (within 24 hours) to the Study Chair.

5.5 **Definition of Dose-Limiting Toxicity (DLT)**

DLT will be defined as any of the following events that are possibly, probably or definitely attributable to protocol therapy. The DLT observation period for the purposes of dose-escalation will be the first cycle of therapy.

Dose limiting hematological and non-hematological toxicities are defined differently.

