If a patient experiences progressive disease at any time point, they must discontinue protocol therapy. Patients with at least a partial response (PR) following Cycle 2 may continue on subsequent cycles of flotetuzumab for a total of up to 6 cycles. Patients should discontinue protocol therapy if they have not achieved at least a PR following Cycle 2. No planned step-up dosing will occur during subsequent cycles unless there is an infusion interruption of > 3 days between cycles of flotetuzumab. For patients with no evidence of disease after Cycle 1, subsequent cycles should be interrupted until ANC $\geq 500 \mu\text{L}$ and platelets $\geq 20,000/\text{mm}^3$. Patients with persistent disease are permitted to continue flotetuzumab regardless of ANC and platelet counts.

Pharmacokinetic sampling and monitoring for ADAs will be performed in all patients (see [Appendix VI-A](#), [Appendix VI-B](#), [Appendix VI-C](#), and [Appendix VII](#)). In consenting patients, correlative studies to characterize the tumor microenvironment will be obtained, which will include peripheral blood studies and bone marrow (see [Appendix X](#) and [Appendix XII](#)). Correlative plasma studies as a measurement of CRS and biomarkers of response will also be obtained in consenting patients (see [Appendix XI](#)).

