5.5.1 Non-hematological dose-limiting toxicity

5.5.1.1 Any Grade 3 or greater non-hematological toxicity at least possibly attributable to protocol therapy with the specific exclusion of:

- Alopecia
- Grade 3 fatigue, anorexia, nausea, vomiting, and diarrhea not requiring hospitalization, tube-feeding, or use of TPN.
- Grade 3 liver enzyme elevation, including ALT/AST, occurring after flotetuzumab administration that returns to Grade ≤ 1 or baseline within 7 days from the start of therapy. Note: For the purposes of this study the ULN for ALT is defined as 45 U/L.
- Grade 3 or 4 fever, febrile neutropenia, or infection
- Grade 3 or 4 isolated electrolyte abnormalities that resolve with or without intervention to \leq Grade 2 within 72 hours. Electrolyte supplementation is encouraged.
- Grade 3 or 4 tumor lysis syndrome that resolves within 7 days without end-organ damage.
- Grade 3 rash that resolves (with or without supportive care) to \leq

THIS PROTOCOL IS FOR RESEARCH PURPOSES ONLY, SEE PAGE 1 FOR USAGE POLICY

Grade 2 within 7 days

- Grade 3 mucositis that resolves (with or without supportive care) to \leq Grade 2 within 7 days
- Early intervention with TPN or enteral tube feeding for anorexia, nausea not attributable to protocol therapy, or concern for poor nutritional status clearly and incontrovertibly not attributable to protocol therapy will not be considered a DLT
- Grade 3 or greater pain due to leukemia, mucositis, typhlitis, infection, or obvious injury
- Grade 3 IRR (including CRS) resolving to \leq Grade 2 within 72 hours. CRS will be defined by ASBMT consensus grading³⁶
- Cases of Hy's law ($> 3x$ ULN of ALT/AST along with $> 2x$ ULN in total bilirubin without evidence of cholestasis) will be considered a DLT if no other reason can be found to explain the observed injury (e.g. leukemia, infection, another drug, etc.).

5.5.1.2 Non-hematological toxicity that causes a delay of ≥ 14 days between treatment cycles.

5.5.1.3 Note: Allergic reactions that necessitate discontinuation of study drug will not be considered a dose-limiting toxicity.

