APPENDIX V: THERAPY DELIVERY MAP FOR CYCLES 2+

Therapy Delivery Map – Cycles 2+ This Therapy Delivery Map (TDM) relates to Cycles 2+. Each cycle lasts 29 days.	Patient COG ID number DOB
--	------------------------------

Criteria to start each cycle are in [Section 5.2](#). Extensive treatment details are in [Section 5.1](#).

This TDM is on 4 pages. Flotetuzumab therapy ends on Day 29 given continuous infusion administration.

DRUG	ROUTE	DOSAGE	DAYS	IMPORTANT NOTES										
IT Cytarabine (ARAC) (all patients)	Intrathecal (IT)	Age-based dosing: 

Age (yrs)	Dose	

< 1	20 mg	

1-1.99	30 mg	

2-2.99	50 mg	

≥ 3	70 mg	

	Age (yrs)	Dose	< 1	20 mg	1-1.99	30 mg	2-2.99	50 mg	≥ 3	70 mg	1	Subsequent doses and timing may be administered at the discretion of the treating physician.
Age (yrs)	Dose													
< 1	20 mg													
1-1.99	30 mg													
2-2.99	50 mg													
≥ 3	70 mg													
Flotetuzumab	Intravenous (IV)	At Cycle 1 target dose	1-28	See Section 5.1 for premedications recommendations. See Section 6 for dose modifications for adverse events.										

NOTE: If a treatment-free interval > 3 days occurs between any 2 cycles, the subsequent cycle will require step-up dosing. If a treatment-free interval > 3 days occurs between any 2 cycles, the Study Chair must be notified and the subsequent cycle dosing schedule must be discussed.

THIS PROTOCOL IS FOR RESEARCH PURPOSES ONLY, SEE PAGE 1 FOR USAGE POLICY

Ht _____ cm Wt _____ kg BSA _____ m² Dose Level _____ nanograms/kg/day

Date Due	Date Given	Day	IT ARAC _____ mg	Flotetuzumab at Cycle 1 Target Dose nanograms/kg/ day	Studies
Enter calculated dose above and actual dose administered below					
		Pre-			a, b, d - g, i - k, m
		1	_____ mg	_____ ng	1, o
		2		_____ ng	
		3		_____ ng	
		4		_____ ng	
		5		_____ ng	
		6		_____ ng	
		7		_____ ng	
		8		_____ ng	
		9		_____ ng	
		10		_____ ng	
		11		_____ ng	
		12		_____ ng	
		13		_____ ng	
		14		_____ ng	
		15		_____ ng	
		16		_____ ng	
		17		_____ ng	
		18		_____ ng	
		19		_____ ng	
		20		_____ ng	
		21		_____ ng	
		22		_____ ng	
		23		_____ ng	c

THIS PROTOCOL IS FOR RESEARCH PURPOSES ONLY, SEE PAGE 1 FOR USAGE POLICY

	24		ng		
	25		ng		
	26		ng		
	27		ng		
	28		ng		
	29			h, n, p, q, r	

Required Observations for Cycles 2+

- a. History. Prior to subsequent cycles.

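### Section 5.3.2 forbids, without exception, the step-up dosing that Section 5.1 and Appendix V require after a between-cycle gap of more than 3 days

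*Combined protocol and SAP*

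**What the plan says.** Section 5.3.2 places intra-patient escalation in the first 7 days of Cycle 1 at DL1 and the first 8 days at DL-1 and DL2, referring to Section 5.1 for the schedule. A separate sentence follows: "Intra-patient dose escalation occurring outside of this time period is not allowed".

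Four other places provide for escalation after Cycle 1:

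- Section 2.5 plans no step-up in later cycles "unless there is an infusion interruption of > 3 days between cycles of flotetuzumab".
- The Section 5.1 narrative says the same: "unless there is an infusion interruption of more than 3 days between cycles of flotetuzumab". It adds that dosing after such an interruption should be discussed with the study chair.
- The note under the Cycles 2+ table in Section 5.1 is mandatory: "If a treatment-free interval > 3 days occurs between any 2 cycles, the subsequent cycle will require step-up dosing".
- Appendix V, the delivery map for those cycles, repeats that note and adds that "the Study Chair must be notified and the subsequent cycle dosing schedule must be discussed".

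Section 5.1 gives the reason for the 3-day limit: short interruptions should reduce disease rebound and "lower the risk for recurrent CRS based upon clinical experience in flotetuzumab-treated adult patients".

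**The concern.** Section 5.3.2 forbids what the Section 5.1 note and Appendix V require. A site that steps up correctly after a long gap departs from the wording of 5.3.2. A site that obeys 5.3.2 omits a measure meant to limit CRS. Section 5.3.2 names no restart dose, but the natural result of leaving out the step-up is a restart at the assigned dose. Cycle 1 is given in hospital. Later cycles may be given to outpatients, so an abrupt restart could happen under less observation.

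Gaps over 3 days are foreseeable. Section 5.2 creates them for responders: "For patients with no evidence of disease after Cycle 1, subsequent cycles should be interrupted until ANC" and platelets reach the stated thresholds. Section 6.2.3 allows up to 21 days beyond the planned start of the next cycle for a dose-limiting non-hematological toxicity to resolve.

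The same sentence in 5.3.2 also leaves no room for a Cycle 1 step-up that is interrupted and finishes after Day 7 or Day 8. Section 8.2.2 and Appendix VI-A anticipate such patients, because they tie pharmacokinetic (PK) samples to when each dose level is actually reached.

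**Working it through.** The plan gives no figure to reproduce. The check compares the texts and then sizes the dose difference.

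**1. Do the two terms mean the same thing?** Section 5.3.2 describes intra-patient escalation by a 7-day window (DL1) and an 8-day window (DL-1, DL2) in Cycle 1. Section 5.1 gives the same windows and calls the procedure step-up dosing. They are one procedure under two names.

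**2. Does the reference to Section 5.1 bring in the exception?** No. It is attached to the sentence describing the Cycle 1 schedule. The prohibition is a separate sentence with no reference and no qualification.

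**3. First-day dose at restart.** The inputs are the assigned doses of 300 (DL-1), 500 (DL1) and 700 (DL2) ng/kg/day from Section 5.3.1, and the Cycle 1 Day 1 dose of 30 ng/kg/day from Section 5.1. The assumption is that a later step-up reuses the Cycle 1 schedule; the protocol leaves that schedule to discussion. The ratio is the restart dose divided by 30.

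| Original level | No dose reduction | After a DLT, one level lower (6.1.1, 6.2.1) |
|---|---|---|
| DL-1 | 300/30 = 10 | no lower level |
| DL1 | 500/30 = 16.7 | 300/30 = 10 |
| DL2 | 700/30 = 23.3 | 500/30 = 16.7 |

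**4. When does the column without reduction apply?** It applies to a gap over 3 days that is not itself a DLT. There are two routes.

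- *Non-hematological delay.* Section 5.5.1.2 begins "Non-hematological toxicity that causes a delay of" and sets the threshold at 14 days or more. A delay of more than 3 and fewer than 14 days that meets no other DLT criterion carries no required reduction.
- *Count-recovery hold.* Section 5.5.2 allows recovery until 42 days after the first treatment day, which is Day 1 + 42 = Day 43. The infusion ends on Day 29, and 43 − 29 = 14. A hold of more than 3 and up to about 14 days carries no required reduction.

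**5. Delayed Cycle 1 step-up.** Section 6.3.1.3 allows the infusion to resume after a Grade 3 reaction that improves within 72 hours. Assume a 3-day stop moves every remaining step by 3 days. The target dose is then reached on Day 7 + 3 = Day 10 at DL1, and on Day 8 + 3 = Day 11 at DL-1 and DL2. Both fall outside the 5.3.2 window.

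**The case against.** The best defence is purposive. Section 5.3.2 sits under the dose-escalation schema, next to the rules for moving between dose levels. Its last sentence may be meant only to stop a patient being taken above the assigned dose. The between-cycle rule is the more specific one and should govern. That is probably what the authors intended, but the text does not say it, and on that reading the sentence still needs rewording.

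Several practical points reduce the weight of the finding, and they stand:

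- Appendix V is the working dosing record for Cycles 2+ and states the step-up requirement. The Study Chair must be notified, so a site that follows it does not choose the restart dose alone.
- Section 5.1 requires prophylaxis, including dexamethasone, before a later cycle when the treatment-free interval exceeds 24 hours. A restart without step-up would still be premedicated.
- The protocol accepts a full-dose restart after gaps of up to 3 days. The ratios above would be the same there, so they describe the size of the dose step and not the added risk from the conflict.
- Few patients may be exposed. Section 2.3.1 reports an adult CR/CRi rate of 5/27. If that rate held among the 27 patients anticipated in Section 11.1, about 27 × 5/27 = 5 could meet the count-recovery hold, and only some would wait more than 3 days. Toxicity delays add an unknown number.

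The Cycle 1 limb is the weaker one. The 3-day shift is assumed, Section 6.3.1.3 has its own rules for resuming the infusion, and an interruption need not push escalation past the window. Appendix VI-A leaves the actual day blank for the step-up samples but pre-prints Day 8 for the sample taken 24 hours after the final step, so it only partly anticipates a delay.

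These points bear on likelihood and size. They do not remove the literal contradiction.

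**Conclusion.** The concern holds: Section 5.3.2 is wrong as written. It bars, without exception, a CRS precaution that Section 5.1 and Appendix V make mandatory after a gap of more than 3 days.

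If the step-up were omitted, the first-day dose would be 10 to 23.3 times the step-up starting dose without a dose reduction, or 10 to 16.7 times after a one-level reduction. Both ranges rest on the assumption that a later step-up starts at 30 ng/kg/day. The number of patients affected cannot be estimated from the documents, and a harmful restart is unlikely given the other instructions.

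The between-cycle conflict leaves the Cycle 1 DLT assessment and the MTD decision untouched. What is at stake is safety at restart in Cycle 2 and later. The correction should be made, but the conflict does not undermine the design.

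**What to change.** Let Section 5.1 and Appendix V prevail. Extend the last sentence of Section 5.3.2 with an exception along these lines: *except step-up dosing required after a treatment-free interval of more than 3 days between cycles (Section 5.1), or completion of a Cycle 1 step-up delayed by a dose interruption*.

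Aligning the softer wording of the Section 5.1 narrative with the mandatory note under the Cycles 2+ table is optional, since the two are compatible.

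The cost is one clause. Sample size, timeline and the planned Cycle 1 schedule do not change.
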